1 BACKGROUND AND RATIONALE

Sporting activity is characterized by factors of the type, duration and intensity of exertion. Depending on the extent of these factors and the associated recovery time, damage to the muscles, signs of inflammation and fatigue in the nervous system occur, as well as energy substrate degradation and local swelling. Therefore, rapid regeneration after intensive sports has become all the more important. According to the meta-analysis by Bleakley et al. 2012, cold is considered one of the most effective recovery methods after sporting activity to delay delayed onset muscle soreness (DOMS). The DOMS are microscopic tears in muscle tissue called exercise-induced muscle damage, which can lead to delayed onset muscle soreness. DOMS usually peak between 24 and 48 hours – sometimes up to 72 hours – after exercise and are characterized by muscle shortening, increased passive stiffness, swelling, decrease in strength and power, localized muscle soreness, and altered proprioception.

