2.2 Primary and secondary endpoints

Primary endpoints

Muscle soreness

A visual analogue scale (VAS) is used for the quantitative assessment of muscle soreness. The muscle soreness of the test subjects is measured on both ventral thighs in 90° knee flexion within 2 seconds. Participants perform a squat at a 90-degree angle and use a hand-held glide scale to choose a value between 0 and 10 cm, with 0 representing no discomfort and 10 representing maximum discomfort. This scale is designed without visible numerical indicators to minimize repetition bias. Measurements are taken during baseline and 24, 48, and 72 hours after the intervention. The examination staff records the selected value in centimetres to document the level of the muscle soreness symptoms felt ventrally.

Inflammation levels

The general inflammation values are determined on the basis of 3 parameters. These are the blood sinking rate, the C-reactive protein and the creatine kinase. These parameters are determined by means of a venous blood draw.

Muscle swelling

Swelling of the ventral thigh muscles is performed using ultrasound diagnostics. The test subjects are in a lying position. Subsequently, a cross-sectional image of the thigh muscles is created and the distance from the femur to the outer boundary of the muscles is measured.

Maximum voluntary isometric muscle contraction

This parameter is measured using an ergometer chair in 90° hip flexion. The test subjects have to try to stretch their thigh as much as possible for 3 seconds. The maximum deflection is used to determine the maximum voluntary isometric muscle contraction.

Secondary endpoints

Superficial skin temperature

The skin temperature of the thighs is measured using the iButton system. The sensors are glued to the skin and continuously measure the temperature of the skin. The data from the sensors is then read out on a computer. This measurement is started during the baseline survey, for the duration of the muscle soreness protocol, and up to 20 minutes after the muscle soreness protocol.

Thermal Perception

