2.3 Investigation design

This study is a single-center, randomized, controlled trial with 3 arms. After the subjects have been admitted to the examination, they are divided into one of the 3 groups.

Group A: immediate cooling according to the muscle soreness protocol

Group B: delayed cooling according to the muscle soreness protocol (24 hours delayed)

Group C: Control group

This examination is a clinical trial of risk category A.

Group A: immediate cooling

In this group, cooling starts immediately after the muscle soreness protocol. Cooling is carried out 3 x /day both on the day of the muscle soreness protocol and for a period of 72 hours. Both thighs are cooled with the "Cold Hot Maxi Pack" from Axanova for a period of 20 minutes.

Cooling log: Day 1 (muscle soreness log, 3x/day), Day 2 (3x/day), Day 3 (3x/day), Day 4 (3x/day)

Group B: delayed cooling

In this group, cooling starts 24 hours after the sore muscle protocol. Cooling is also carried out 3 x /day for a period of 72 hours. Both thighs are cooled with the "Cold Hot Maxi Pack" from Axanova for a period of 20 minutes.

Cooling log: Day 1 (muscle soreness log, no cooling), Day 2 (3x/day), Day 3 (3x/day), Day 4 (3x/day).

Group C: Control group

This group receives according to the muscle soreness protocol and will not receive any cooling intervention, nor any other intervention, for the entire period thereafter.

Sore muscle protocol

To induce sore muscles, the test subjects perform one-sided, 6 times 12 – 15 knee extensors on an ergometer chair. They straighten and bend the knee as far as possible. They repeated the exercise 5 more times after a 2-minute break (a total of 6 rounds). The movement sequences are observed and corrected if necessary. A similar protocol has already been successfully used in the literature to induce muscle soreness (Ruas et al 2022, Comparison between eccentric-only and coupled concentric-eccentric contractions for neuromuscular fatigue and muscle damage). In order to increase the significance of the investigation, the subjects are asked not to carry out any additional interventions during the experimental phase.

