3.3 Investigation procedures

Investigation duration:

Subject to EC approval in 2024.

Recruitment period: January 2025

Conduct of the study: February - March 2025

Statistics and writing of the article: April – July 2025

Individual Investigation duration for each participant

Phase	Content	Time
Recruitment	Handing out patient information & consent, explanation of the experiment	30 min
Experiment Day 1	Anthropometry, baseline measurement, muscle soreness protocol (cooling: group A)	60 min
Experiment Day 2	Follow-up measurement 24 hours (Cooling: Group A and Group B)	30 min
Experiment Day 3	Follow-up measurement 48 hours (Cooling: Group A and Group B)	30 min
Experiment Day 4	Follow-up measurement 72 hours (Cooling: Group A and Group B)	30 min
Total time required per subject		180 min

Recruitment

As soon as the potential test subjects show interest in the study and arrive at the laboratory in Landquart, they are sent to the study director. If he is not present or available at that time, interested parties are asked to appear on another day.

The head of the study explains the procedure, the tests carried out, the risks and possible inconveniences. In addition, it is explained that participation is voluntary and that withdrawal is possible at any time, without giving reasons, without this having a negative impact on future care. The test subjects then receive the test subject information, which describes the examination in detail and in an understandable way. The document also contains a checklist that must be completed. The declaration of consent is also provided and must be signed and returned by the Director of Studies before the start of the programme. The doctor checks the completed checklist and confirms the consent.

Baseline measurements

The room temperature and relative humidity are determined at the beginning of each measurement day (Voltcraft MT52 digital multimeter, Hirschau, Germany). Baseline measurements include demographic data (age, gender, height). Anthropometric features at the beginning of the study included height (GPM Stadiometer, Zurich, Switzerland), body mass, and body fat percentage estimation. Body mass and lower body fat percentage were measured using

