The subjects in group A (immediate cooling) receive the first cooling on the two thighs immediately after the end of the muscle soreness protocol. This cooling is carried out in the supine position. After this application, you can leave the laboratory and the measurement of the skin temperature is stopped.

Group B (delayed cooling) and group C (control group) do not receive any cooling (group B) or any intervention (group C) immediately after the muscle soreness protocol. However, you will also need to spend 20 minutes lying on your back in the lab before the skin temperature measurement is completed.

Follow-up measurements

Follow-up measurements will be taken for each measurement in the same order as for the baseline measurement ((1) Inflammatory markers, (2) Muscle swelling, (3) Soreness of muscles, (4) Maximum voluntary isometric contraction). The follow-up measurements take place 24, 48, and 72 hours after the muscle soreness protocol in the laboratory in Landquart.

The measurement method and the equipment used for each specific result are described in Chapter 3.2.

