δ_i	The difference between the i th treatment agent and the control agent ($\mu_i - \mu_c$) for which the test strength is calculated.
σ	The standard deviation of the responses within each group.
Alpha	The probability of rejecting the null hypothesis that the control mean is equal to the treatment mean described in this row.

Summary statements

A parallel 3-group design (with a control group and 2 treatment groups) is used to test whether the mean for each treatment group is different from the mean of the control group ($H_0: \delta = 0$ versus $H_1: \delta \neq 0, \delta = \mu_i - \mu_c$). The hypotheses are evaluated using two two-sided, two-sample methods. Bonferroni-adjusted t-tests with the same variance and an overall (experimental) Type I error rate (α) of 0.05. The common standard deviation for all groups is assumed to be 2.1. The mean value of the control group is assumed to be 4.72. The treatment means 2.21 and 1.87 with at least 80% test strength to be detected in each case. For the test, the (same) group sample size needed for each of the three groups (control and treatments) is 13 (39 subjects in total). The group sample sizes were calculated using PASS 2023, version 23.0.1.

Sample size taking into account the dropout rate

Group	Dropouts Abandonment Rate	Number of cases/group	Number of cases with drop-out rate	Number of abandoned participants
1 - 3	10%	13	15	2
Total	n/a	39	45	6

Taking into account the drop-out rate

Taking into account a dropout rate of 10%, the group sizes in each study arm should be 15 subjects.

Statistical approach to examine the primary endpoints

The statistical analysis is performed using IBM SPSS Statistics (version 27, IBM Corp., Armonk, NY, USA) and the significance level is set to $p < 0.05$.

In order to be able to determine the differences between groups, a repeated ANOVA analysis is carried out with a factor of 1: time (baseline, 24 hours, 48 hours, 72 hours) and a factor of 2:

intervention (group A, group B, group C) for the recovery parameters (inflammation values, muscle swelling, muscle soreness data, maximum voluntary isometric muscle contraction).

The examination is discontinued if the participants are intolerant to the local cold application. Participants in the IC and DC groups are instructed to cancel a cooling session and contact their contact immediately if they experience symptoms such as severe pain/discomfort as a result of the cooling.

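### Group B is scheduled to start cooling only at about its 24 h visit, but section 4.1 treats 24 h as an ordinary follow-up level and names no tested term or visits, so a group main effect or visit average would dilute B versus control

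*Combined protocol and SAP*

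**What the plan says.** Section 4.1 gives one analysis for all primary endpoints: "a repeated ANOVA analysis is carried out with a factor of 1: time (baseline, 24 hours, 48 hours, 72 hours"), crossed with intervention at three levels (A, B, C), at a significance level of 0.05. It names no tested term, contrast, post-hoc test or deciding visit, and it gives 24 h no special role.

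Section 2.3 says of group B: "In this group, cooling starts 24 hours after the sore muscle protocol". Its log reads "Day 1 (muscle soreness log, no cooling), Day 2 (3x/day), Day 3 (3x/day), Day 4 (3x/day"). Section 3.3 has groups B and C both rest supine for 20 minutes after the exercise, with no cooling.

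On the timing of measurements, section 3.3 says "The follow-up measurements take place 24, 48, and 72 hours after the muscle soreness protocol in the laboratory in Landquart", whereas section 2.2 says of soreness "Measurements are taken during baseline and 24, 48, and 72 hours after the intervention". The Day 2 row of the duration table in 3.3 reads "Follow-up measurement 24 hours (Cooling: Group A and Group B"), without giving an order. Section 2.4 places the 24 h application at home.

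The sample-size table in 4.1 assumes differences from control of -2.51 cm (A) and -2.85 cm (B), with SD 2.1 and 13 per group. It ties these differences to no visit.

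**The concern.** Up to about the 24 h visit, B and C are scheduled to be handled alike. Apart from chance, and from whatever effect a single early session might have, the B-C difference at that visit should be near zero. A group effect that averages over visits including 24 h therefore pulls B towards control at a visit where A has already been cooled. Delayed cooling could then look weaker than it is, both against control (the first hypothesis in section 2.1) and against immediate cooling (the second).

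The 24 h visit is also informative in its own right. Section 1 notes that "DOMS usually peak between 24 and 48 hours", so B's 24 h value could be a reading taken after the exercise and before cooling, when soreness is near its height. The baseline reading cannot serve this purpose because it precedes the exercise. The plan does not say how the 24 h value is to be used.

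**Working it through.** **Inputs from section 4.1.** SD 2.1; 13 per group; two-sided alpha 0.05 without Bonferroni divisor, as in the table; differences from control of 2.51 cm (A) and 2.85 cm (B), shown here as reductions.

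**Assumptions, not in the documents.** Equal SD at every visit and equal correlation ρ between visits, at 0.3, 0.5 and 0.7. The effect is constant once cooling has started. For baseline, 24, 48 and 72 h the effects are then A = 0, 2.51, 2.51, 2.51 and B = 0, 0, 2.85, 2.85.

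**Step 1: the plan's figures.** The standard error is 2.1 × √(2/13) = 0.824. The noncentral t distribution with 24 df gives power 0.832 for 2.51 cm and 0.913 for 2.85 cm. Both match the table.

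**Step 2: B versus C by choice of visits.** The mean of k visits has SD 2.1 × √[(1 + (k − 1)ρ)/k], and the standard error is that SD × √(2/13). Example for four visits at ρ = 0.5: SD = 2.1 × √(2.5/4) = 1.66; SE = 0.651; effect = (0 + 0 + 2.85 + 2.85)/4 = 1.425; ratio 2.19; power 0.56.

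| Visits averaged | B-C effect (cm) | Share of 2.85 | Power at ρ = 0.3 / 0.5 / 0.7 |
|---|---|---|---|
| All four (group main effect) | 1.425 | 50% | 0.67 / 0.56 / 0.47 |
| 24, 48, 72 h | 1.90 | 67% | 0.86 / 0.77 / 0.70 |
| 48, 72 h | 2.85 | 100% | 0.98 / 0.97 / 0.95 |

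**Step 3: A versus B.** Over four visits A keeps 3/4 of its effect: 0.75 × 2.51 = 1.88 cm. A then looks better than B by 1.88 − 1.425 = 0.46 cm. At 48 and 72 h, under the plan's own means, B is better by 2.85 − 2.51 = 0.34 cm. The direction depends on which visits count.

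**Step 4: the interaction.** The group-by-time test (6 and 108 df, sphericity assumed) has power 0.978 / 0.998 / above 0.999 under the same effects. It is not diluted, because B's late start is part of the signal.

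**Step 5: the 24 h value as covariate for B versus C.** The residual SD of the 48/72 h mean is 2.1 × √[(1 + ρ)/2 − ρ²]. It falls from 1.69 / 1.82 / 1.94 to 1.57 / 1.48 / 1.26, and power at 2.85 cm becomes 0.993 / 0.997 / above 0.999. All options are near the ceiling at that effect, so a smaller one separates them better. At an illustrative 2.0 cm (my choice, not the plan's), power is 0.87 / 0.91 / 0.97 with the covariate, 0.65 / 0.81 / 0.97 for the interaction restricted to B and C, and 0.39 / 0.31 / 0.26 for the four-visit main effect.

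**Step 6: A at 24 h against B and C combined (13 v 26).** SE = 2.1 × √(1/13 + 1/26) = 0.713, against 0.824 for A v C. Power at 2.51 cm rises from 0.83 to 0.93.

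**The case against.** The strongest reply is that the ANOVA in 4.1 includes an interaction, and the interaction is the natural test of different recovery courses. It is not diluted, and it already uses B's baseline and 24 h values within subject. That stands. A reader might infer that the plan as written dilutes B's effect, or that B's 24 h data are wasted. The documents support neither, because dilution arises only if the main effect or a visit average decides. What remains is that the plan does not name the interaction as the test. A 6-df omnibus result would still need contrasts at named visits before it could speak to B versus C or A versus B.

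Second, it is tempting to say flatly that B is uncooled at 24 h. The schedule makes this likely but does not establish it. The duration table gives no order for Day 2, the application is at home while the measurement is in the laboratory, and section 2.2 times soreness from the intervention, which for B could be a different clock.

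Third, B's first uncooled day belongs to the delayed strategy. An advantage of A at 24 h is a genuine consequence of cooling at once, and the second hypothesis asks about exactly that. Removing 24 h from A versus B would change the question, so this point does not ask for it.

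Fourth, pooling B with C and adjusting for the 24 h value are gains in precision. A versus C at 24 h is valid as it stands and, at 0.83, meets the plan's 80% target. Soreness is self-rated and the trial is unblinded, so B, expecting to be cooled, may not rate exactly as C does.

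**Conclusion.** The point holds in conditional form. By the schedule, the planned 2.85 cm cannot be expected for B at 24 h, and 4.1 leaves open an analysis that would average it in. If the group main effect were used, B versus C would fall to 50% of the planned effect, power would be 0.47 to 0.67 instead of 0.95 to 0.98 on 48/72 h, and A versus B could change direction. If the interaction were used there would be no dilution, but neither hypothesis would be answered without further contrasts.

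The 50%, 67% and 100% shares rest only on a constant effect once cooling starts and none before. The powers also rest on the assumed correlations and on an equal SD at every visit. Near-zero soreness before exercise would make the baseline SD smaller and change the powers that involve baseline, but not the shares. This is worth correcting before analysis. It does not invalidate the design or the data to be collected.

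**What to change.** In section 4.1:

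- **B versus C:** estimate from the mean of 48 and 72 h, with the 24 h value as covariate. Use this covariate for B versus C only, since in A the 24 h value is already post-treatment.
- **A versus B:** keep 24 h as part of the immediate-versus-delayed comparison, report it separately from 48/72 h, and state which decides.
- **A at 24 h (optional):** compare with B and C combined for precision, and show A versus C alongside because the trial is unblinded.

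Reconcile the synopsis and sections 2.2, 2.4 and 3.3 on the order of measurement and cooling on Day 2, and on whether visits are timed from the intervention or from the soreness protocol. The 24 h covariate and the pooling are valid only if B is in fact measured before its first cooling.

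The cost is wording: no added subjects, visits or measurements. The one downside is that B versus C then describes cooling from 24 h onward and not the whole 72 h.

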a TANITA-TBF 611 scale (Tokyo, Japan). The estimate of the percentage of lower body fat was chosen because the cold pack was applied to the thigh, which mainly affects the lower extremities. Recovery parameters (see Exact Measurement Method and Primary and Secondary Endpoints) are assessed in the same order for each measurement: (1) Inflammation Scores, (2) Muscle Swelling, (3) Soreness, (4) Maximum Voluntary Isosomic Muscle Contraction. The measurement method and the equipment used for each specific result are described in Chapter 3.2.

Randomization

The randomization of the subjects will take place on the day of the baseline measurement by drawing a lot. It is ensured that the same number of tickets are available for each intervention group (5 tickets per group) and test subjects. If the number of subjects in a group exceeds one third of the total number of subjects, the lots of this group will be removed. In order to ensure the equality of the groups in terms of covariates and gender, the composition of the groups is monitored. As soon as half of a group consists of male or female subjects, the tickets for this group are removed for future subjects of the same sex.

The tickets are made of folded paper with the numbers 1, 2 or 3 on them and are placed together in a container. The drawing of the lots is carried out by the test persons themselves. After the draw, the subjects hand over the unread ticket to the study director, who assigns them to a group.

Blinding

Since cold applications are tested in this study, blinding is not possible.

Sore muscle protocol

To induce muscle soreness, a one-legged knee extensor protocol is used, which has already been used (Ruas et al., 2022). Participants will be instructed to straighten and bend their knee for 6 sets for 12 – 15 reps, with 2 minutes rest between sets. During the 2-minute break, the participants are allowed to sit on the chair. The execution of the knee extensor protocol is visually observed by an examiner. Verbal corrections of the execution can be given by the examiner. However, no verbal encouragement is given. All training sessions are carried out in the morning. If a participant is unable to perform all the repetitions of a set due to extreme fatigue or maximum effort, the set can be stopped and a new set can be started after the rest period. However, at least 12 repetitions per set must be performed. Otherwise, this will be considered an abandonment.

Intervention

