6 FURTHER ASPECTS

6.1 Overall ethical considerations

The study is carried out on healthy volunteers. Participants can opt out of the investigation at any time without consequences, as indicated in the informed consent form. The sample of healthy participants between the ages of 18 and 30 reflects a population that engages in regular physical activity, so the results are transferable to the general population. To prioritize the safety of participants, vulnerable populations such as pregnant women and those with certain health conditions were excluded to minimize possible adverse reactions. The results of this research can provide valuable insights into the mechanisms and application of recovery strategies after exercise. The use of a randomized controlled trial design is scientifically rigorous and minimizes bias. By considering covariates (e.g., gender) in randomization, the study increases internal validity and reduces the potential for confounding variables. The informed consent form explicitly states that participants will be informed of personal findings and random results relevant to their health (e.g. abnormal blood values).

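### Allocation is balanced by sex but the ANOVA leaves sex out, so between-subject group comparisons are conservative and less efficient than they could be

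*Combined protocol and SAP*

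**What the plan says.** The Randomization text in section 3.3 describes a draw of lots that is restricted by sex: "As soon as half of a group consists of male or female subjects, the tickets for this group are removed for future subjects" of that sex. The stated purpose is balance: "In order to ensure the equality of the groups in terms of covariates and gender, the composition of the groups is monitored". Sex is the only covariate with an operating rule. Section 6.1 relies on the restriction as a strength of the design: "By considering covariates (e.g., gender) in randomization, the study increases internal validity and reduces the potential for confounding variables".

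Sex is available for the analysis. Section 3.3 states "Baseline measurements include demographic data (age, gender, height"), and section 7.2 lists gender among the items recorded in the CRF.

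The analysis in section 4.1 has two factors. The first is given as "a repeated ANOVA analysis is carried out with a factor of 1: time (baseline, 24 hours, 48 hours, 72 hours"). The second is "intervention (group A, group B, group C) for the recovery parameters", tested at the 0.05 level. No sex factor, covariate or stratified analysis appears anywhere. The plan also does not say whether the group main effect, the group-by-time interaction or pairwise contrasts decide the hypotheses in section 2.1.

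**The concern.** When allocation is forced to balance a factor that affects the outcome, the true sampling variance of a group difference no longer contains that factor's contribution. A model that omits the factor still estimates the residual variance with the contribution included. The standard error is then too large, the p-values are too large, and the test runs below its nominal 5%. The restriction in section 3.3 has already bought precision that the model in section 4.1 does not use.

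This could matter for endpoints on which men and women differ in level. Isometric strength in kg and muscle thickness in cm are plausible candidates, but the documents give no sex-specific means or SDs for any endpoint. With 45 subjects there is little precision to spare. Only soreness has a sample-size calculation, so the other primary endpoints have no planned power to fall back on.

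**Working it through.** **1. The plan's own figure.** Inputs from section 4.1: 13 per group, SD 2.1, differences 2.51 and 2.85, two-sided alpha 0.05, no Bonferroni divisor in the table. The noncentrality is 2.51 / (2.1 × √(2/13)) = 3.05 with 24 df, giving power 0.8323. For 2.85 it is 3.46, giving 0.9129. Both match the stated 0.83233 and 0.91287. Then 13 / 0.9 = 14.4, rounded up to 15 per group. The SD of 2.1 is not split by sex.

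**2. Size of the effect on a between-subject comparison.** Assume men and women differ by d within-sex SDs, 15 per arm, and sexes balanced within arm. The sex difference adds about 45 × d²/4 to the error sum of squares, which has 45 − 3 = 42 df. The error variance is inflated by

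1 + (45 × d²/4) / 42 = 1 + 0.268 d²

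while the true variance of the group difference is unchanged. The standard error ratio is √(1 + 0.268 d²). The nominal critical value (t with 42 df) is 2.018, so the test in effect uses 2.018 times this ratio.

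| Assumed d | Share of variance due to sex, (d²/4)/(1 + d²/4) | SE ratio | Effective critical value | True type I error |
|---|---|---|---|---|
| 1 | 0.20 | 1.13 | 2.27 | 2.8% |
| 1.5 | 0.36 | 1.27 | 2.55 | 1.4% |
| 2 | 0.50 | 1.44 | 2.90 | about 0.5% |

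Simulation (40,000 runs, 7/8 of each sex per arm, subject means analysed with and without sex) gave type I errors of 0.028, 0.014 and 0.005 without sex, and 0.049 to 0.051 with it. For an effect of 1.05 within-sex SDs, power was 0.80 with sex in the model and 0.72, 0.63 and 0.50 without. With no sex difference the two were 0.804 and 0.805.

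**3. The planned ANOVA.** This was simulated with 3 groups × 4 times, 14 per group, an assumed within-subject correlation of 0.5, and a sex difference constant over time. There were 20,000 null runs, and 10,000 runs with a 0.7 SD post-baseline shift in both cooling groups.

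| Variance share of sex | Main effect, type I error without / with sex | Main effect, power without / with sex | Group-by-time, type I error without / with sex | Group-by-time, power without / with sex |
|---|---|---|---|---|
| 0.1 | 0.030 / 0.049 | 0.35 / 0.44 | 0.047 / 0.048 | 0.485 / 0.486 |
| 0.2 | 0.014 / 0.048 | 0.30 / 0.48 | 0.051 / 0.050 | 0.541 / 0.540 |
| 0.3 | 0.006 / 0.048 | 0.24 / 0.53 | 0.049 / 0.049 | 0.609 / 0.609 |

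The main effect shows the problem. The interaction does not, because a constant sex difference cancels out of within-subject changes.

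**4. When the interaction is affected.** If sex also changes the time course, with an assumed sex-by-time share of 0.02, 0.05 or 0.10, the interaction's type I error without sex falls to 0.035, 0.021 or 0.008. With sex and sex-by-time in the model it stays at about 0.05.

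**5. The stated power.** If 2.1 is the total SD, the unadjusted t-test under sex balance has power 0.833 to 0.898 at 13 per group for variance shares of 0 to 0.5. That is no lower than the plan states. With sex in the model the range is 0.832 to 0.985.

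**The case against.** The strongest counter-argument is that the test closest to the research question is not affected. Section 2.1 asks about recovery, and baseline is a level of the time factor, so a difference in recovery is the group-by-time interaction. That is tested against within-subject error, where a constant sex difference cancels. The group main effect averages in the pre-treatment baseline and is the weaker test: in step 3 the interaction without sex has more power than the main effect with sex. This stands, and it limits the point to between-subject comparisons. It does not remove it, because the plan names no decisive effect and sizes the trial on two-sample comparisons of group means.

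A reader might infer that all the planned group tests miss their 5% level. The documents do not support that: for group-by-time it would need a sex-by-time effect, on which they are silent. A reader might also infer that the trial falls short of its stated power. It does not, if 2.1 is the total SD; the loss is relative to a model with sex. Nor is there a risk of false claims of benefit, since the error is in the conservative direction.

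Two further reservations stand. The sex differences used here are assumptions. The balance is also only approximate: 15 is odd, and section 4.2 does not replace drop-outs.

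**Conclusion.** The mismatch between a sex-restricted draw and a model without sex is plain in the text. Its consequence is confined to the group main effect and to group contrasts at single time points. There the plan gives up efficiency and the nominal level in proportion to how much sex explains: nothing if sex is unrelated to the endpoint, and the losses shown in steps 2 and 3 if it is related. Those sizes rest on assumed sex differences of 1 to 2 within-sex SDs, or assumed variance shares of 0.1 to 0.3, and on near-complete balance. The direction does not depend on the exact values. This is a cheap gain in efficiency and in the accuracy of the stated level. It is not a threat to the validity of a positive result.

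**What to change.** In section 4.1, prespecify sex as a second between-subjects factor, together with sex-by-time, in the same SPSS repeated-measures model for every primary endpoint. Take both the group and the group-by-time results from that model, and report the model without sex as a sensitivity analysis. A sex-by-group test is not needed. The choice should be written down before the data are seen, since the trial is unblinded and adding sex later could look selective.

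The cost is a sentence or two in section 4.1. With 45 completers, the between-subject error df fall by one, from 45 − 3 = 42 to 41. The within-subject error df fall by three, from 42 × 3 = 126 to 41 × 3 = 123. Sex is already recorded, so no new data are needed.
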